6. Willing to be contacted by research team

Exclusion Criteria

1. Patients who do not want to participate in the telemedicine visit
2. Adults unable to read and write English. The PAM study is only in English at this time
3. Patients that do not have a home phone or home internet. This is needed to do follow up and any follow up telemedicine visits
4. Patients that do not have a smart phone or computer that can connect to the internet

PROTOCOL TITLE: Implementation of Telemedicine for patients with wounds and ulcers.

We do not plan to include:

- Pregnant women- low incidence of wounds in these patients due to PAD and DM
- Prisoners- Cannot accurately determine care and outcomes

Number of Subjects:

Rural Health Clinic A	25
Rural Health Clinic B	25
Rural Health Clinic C	25
Rural Health Clinic D	25
Rural Health Clinic E	25
Total Number of Patients	125

We plan to include 25 subjects at each of the 5 out of network clinics that are referred to the UC Davis Vascular Clinic for telehealth services for a total enrollment of 125 patients.

5) Study Timelines

The Screening and follow up of data of all patients will start approximately from 5/01/2020 – and end 12/31/2021

Review and Analysis should will be completed by approximately 06/30/2022

6) Study Endpoints

The primary endpoint for this study is time to specialty consultation.

Secondary endpoints are time to revascularization, time to other specialty consultation, time to wound healing, number of telemedicine visits, major amputation, number of hospitalizations, number of emergency room visits, and number of in person visits.

PROTOCOL TITLE: Implementation of Telemedicine for patients with wounds and ulcers.

7) Procedures Involved

Screening: Patients referred from rural clinics will be screened when they are referred to the UC Davis Vascular Clinic for telehealth services to determine if they meet the inclusion/exclusion criteria.

Enrollment/Procedures at Baseline Telehealth Visit: Patients receiving telehealth services will follow the standard operating procedures for those visits. Which includes asking new patients to complete the UCD Privacy statement for new patients and a patient activation questionnaire on the day of their telemedicine visit.

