Follow-Up Post Telehealth Visit: All patients will be contacted every 4 weeks to determine if they have had a procedure for their leg wound (revascularization) and if the wound has healed. Patients will be followed until they reach a secondary study end-point which is wound healing, amputation, or for a maximum of 12 months.

8) Withdrawal of Subjects

Patients who choose not to participate in completing a patient activation questionnaire will not be included in this QI project. Patient care is not directed in this project and is clinical driven per standard of care and standard operating procedures for the Vascular Clinic.

9) Risks to Subjects

This is a minimal risk study and the only risk foreseen is a potential breach of confidentiality which will be minimized by securing the data as outlined in the protocol.

10) Potential Benefits to Subjects

No direct benefits to the patient will occur during the data collection and review of the QI project. Future patients may receive a benefit from increased access to telehealth visits or proven to shorten time to care for patients referred from rural clinics.

PROTOCOL TITLE: Implementation of Telemedicine for patients with wounds and ulcers.

Statistical Analysis Plan: Changed as a result of COVID and removal of the comparison arm of the study

The data will be analyzed by Kaplan-Meier analysis comparing time to specialty visit for patients who underwent telemedicine visits to those who did not. Secondary outcome analysis will include chi-squared analysis of the proportion of patients that had wound healing in the telemedicine group compared to those that did not have a telemedicine visit, and Kaplan-Meier analysis of time to definitive revascularization and wound healing for patients that underwent telemedicine and were treated at UCD.

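### The healing comparison names no comparator, and the Kaplan-Meier analyses of healing and revascularization lack a censoring and competing-event rule

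*Combined protocol and SAP*

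**What the plan says.** The Statistical Analysis Plan opens by stating that it was "Changed as a result of COVID and removal of the comparison arm of the study". Its secondary analyses are then:

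- a chi-squared test of the "proportion of patients that had wound healing in the telemedicine group compared to those that did not have a telemedicine visit";
- "Kaplan-Meier analysis of time to definitive revascularization and wound healing for patients that underwent telemedicine and were treated at UCD".

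Section 7 (Follow-Up Post Telehealth Visit) has patients contacted every 4 weeks to "determine if they have had a procedure for their leg wound (revascularization) and if the wound has healed". It then says: "Patients will be followed until they reach a secondary study end-point which is wound healing, amputation, or for a maximum of 12 months".

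The list of secondary endpoints in section 6 includes "time to wound healing, number of telemedicine visits, major amputation, number of hospitalizations", as well as time to revascularization. It speaks of major amputation, whereas the stopping rule in section 7 speaks of amputation without qualification.

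Section 5 gives the calendar: "The Screening and follow up of data of all patients will start approximately from 5/01/2020", ending 12/31/2021. The plan is "for a total enrollment of 125 patients" (section 4, Number of Subjects).

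Nowhere do the documents state a censoring rule, a competing-event rule, the quantity that the curves are meant to estimate, or how death is handled. They do not define being treated at UC Davis.

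**The concern.** There are two faults, and the first is the clearer.

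**The healing comparison.** The comparison group no longer exists within the study. Section 4 admits only patients willing to be seen by telemedicine. The historical reference in the sample-size paragraph is a median time to consultation and says nothing about healing. The proportion healed also has no stated time point. A patient enrolled after 12/31/2020 cannot complete 12 months by the end of data collection, so a crude proportion read as a 12-month figure would be too low.

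**The Kaplan-Meier curves.** Contact ends at healing or amputation, and a routine analysis would censor there. Kaplan-Meier then treats the departed patient as someone who could still have the event at the same rate as those who remain. For healing, that is untrue of patients who were amputated or died. For revascularization, it is untrue after amputation or death, and may be untrue after healing. One minus Kaplan-Meier (1-KM) then exceeds the share of patients who have the event.

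At stake is the reading of two secondary endpoints. One of them, time to definitive vascular treatment, is in the study hypothesis.

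**Working it through.** The plan gives no rate, sample size or power for healing or revascularization, so there is no stated figure to reproduce. Every rate below is an assumption for all enrolled patients.

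**1. Formula, constant hazards over 12 months.** Let p be the 12-month proportion observed to have the event first and c the proportion with a competing event or stop first.

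- Total cumulative hazard: H = -ln(1 - p - c)
- Event hazard: r = H × p/(p + c)
- 1-KM with the competing patients censored: 1 - exp(-r)

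Example, p = c = 30%: H = -ln(0.40) = 0.916; r = 0.458; 1-KM = 1 - exp(-0.458) = 36.8%, an excess of 6.8 points.

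**2. Healing (competing: amputation plus death).**

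| Healed | Amputation + death | 1-KM | Excess (points) |
|---|---|---|---|
| 40% | 2% | 40.5% | 0.5 |
| 50% | 5% | 51.6% | 1.6 |
| 60% | 5% | 62.1% | 2.1 |
| 50% | 10% | 53.4% | 3.4 |
| 60% | 20% | 70.1% | 10.1 |

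**3. Revascularization, if nobody is revascularized after healing.** Here c covers healing without revascularization, amputation and death.

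| Revascularized | Competing | 1-KM | Excess (points) |
|---|---|---|---|
| 20% | 20% | 22.5% | 2.5 |
| 30% | 30% | 36.8% | 6.8 |
| 40% | 40% | 55.3% | 15.3 |
| 40% | 50% | 64.1% | 24.1 |

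**4. Revascularization, if it can still occur after healing.** Healing ends observation; it does not prevent the event. Suppose 5 of the 30 competing points are amputation or death, with hazard a = 0.916 × 5/60 = 0.076, and that hazards do not change at healing. The true 12-month share is then r/(r + a) × [1 - exp(-(r + a))] = 0.458/0.535 × (1 - exp(-0.535)) = 35.5%. Against 36.8%, the excess is about 1 point instead of 6.8.

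The same calculation for 40%/40% has r = 0.805 and a = 1.609 × 5/80 = 0.101. The true share is 0.889 × (1 - exp(-0.905)) = 52.9%, against a 1-KM of 55.3%.

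**5. Timing.** If all revascularization falls in months 0-3 and competing events start only after month 3, nobody is removed while events accrue and the excess is zero. If competing events run over months 0-12, the excess is 0.7 points at 20%/20% and 7.8 at 40%/50%, again with no revascularization after healing.

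**6. Crude healed proportion.** The calendar window is 20 months, so a patient enrolled at month u has min(12, 20 - u) months of follow-up. Assume 60% truly healed by 12 months at a constant hazard, no amputation or death, and uniform enrolment over L months.

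For L = 20, 8/20 of patients have the full 12 months and contribute 0.40 × 60% = 24.0%. The other 12/20 average 1 - 0.6/0.916 = 34.5% and contribute 20.7%. The total is 44.7%.

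| Enrolment period | Under 12 months' follow-up | Crude healed |
|---|---|---|
| 8 months | 0% | 60.0% |
| 10 months | 20% | 59.4% |
| 14 months | 43% | 55.4% |
| 20 months | 60% | 44.7% |

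The 20-month row is the extreme, in which the last patient has no follow-up.

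**The case against.** The strongest reply is that the Kaplan-Meier fault is conditional. The plan never says that patients will be censored at healing or amputation, nor that the curve will be read as a proportion. If patients with a competing event stay in the risk set to 12 months, the bias does not arise. This stands: the documents show an unspecified rule and target, not an estimator that must be wrong. The stopping rule does, however, lead naturally to censoring at last contact unless the plan says otherwise.

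A reader might infer that the 2.5 to 24 points in step 3 are the bias for revascularization. The documents do not support that, because those figures need the extra assumption that no one is revascularized after healing. Nor do they support the inference that the curve would show a median time although fewer than half are revascularized. At 40%/40% with unchanged hazards, the true share is already above half (step 4).

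The analysis is limited to patients treated at UC Davis. If that means revascularized there, every analysed patient has the event, and the problem is selection, not competing risk. This stands as a reason to define the phrase.

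The weight is limited. These are secondary, descriptive, single-group curves in a minimal-risk project. At n = 125 and 30%, the 95% half-width is 1.96 × √(0.3 × 0.7/125) = 8.0 points, larger than the 6.8-point example. The error is systematic, though, and a larger sample would not remove it.

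None of this answers the chi-squared contradiction, which needs no competing-risk argument. Section 5's dates are approximate, so the shortfall in the crude proportion depends on how enrolment actually ran.

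**Conclusion.** The point holds in two parts of different strength.

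- **Wrong as written:** the chi-squared healing comparison contradicts the plan's own heading and has no named source of comparator data. Its proportion has no fixed time point and understates 12-month healing if enrolment ran past 12/31/2020. With 60% truly healed, the shortfall is 0 to about 15 points depending on the enrolment period.
- **Conditional:** if patients are censored when contact stops, 1-KM overstates both shares. For healing, the assumed cases give about 0.5 to 2 points at 2-5% amputation plus death, and up to 10 points at 60%/20%. For revascularization, the excess is greatest if no one is revascularized after healing. It shrinks towards the amputation and death part alone if the hazard is unchanged, and can be near zero if revascularization is early.

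The true size cannot be derived from the documents. The primary endpoint, time to specialty consultation, is not affected by this point. The plan should be changed because the repair is cheap, with medium confidence that the effect would be material.

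**What to change.** 1. Remove the chi-squared comparison, or name the external comparator and fix the time point at 12 months.
2. For healing, report the 12-month cumulative incidence by Aalen-Johansen with a 95% confidence interval, with amputation and death as competing events.
3. For revascularization, choose one target and say so. Either define it as revascularization before healing, with healing, amputation and death as competing events; or keep collecting revascularization to 12 months after healing, with only amputation and death competing. Aalen-Johansen with healing as a competing event does not estimate all revascularization by 12 months if some occurs after healing.
4. Censor only at loss to follow-up, 12 months or data cut-off.
5. Reconcile the amputation that ends follow-up in section 7 with the major amputation listed in section 6, and state which is the competing event.
6. Report in all enrolled telemedicine patients. Define being treated at UC Davis, and keep any analysis limited to those patients supplementary.

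**Cost.** Steps 1 to 6 need SAP wording, two definitions and standard software. The second option in step 3 also needs continued contact after healing. Dates of amputation and death must be obtained. Death needs a source other than the patient contact, and some dates must be collected retrospectively because this protocol version (March 2021) postdates the planned start (about May 2020). The estimates will be lower than 1-KM, and the two-group healing test is lost unless a comparator is named.

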PROTOCOL TITLE: Implementation of Telemedicine for patients with wounds and ulcers.

1) Protocol Title

Title: Implementation of Telemedicine for patients with wounds and ulcers.

Protocol Version Date: March 11th, 2021

2) Objectives:

The objective of this quality improvement project is to assess if telemedicine can improve the quality of specialty care offered for new patients with wounds and ulcers due to peripheral artery disease (PAD) and diabetes mellitus (DM) at RHCs. The specific aims of this project are:

- a) Implement telemedicine consultations at rural health clinics.
- b) Evaluate the effect of telemedicine consultation to improve time to specialist evaluation and time to definitive treatment for patients with wounds and ulcers in rural clinics.
- c) To determine if patients with lower levels of activation need more resources to help get care when offered telemedicine

Hypothesis: *Telemedicine consultation can decrease mean time to specialist consultation and time to definitive vascular treatment by 50%. Use of telemedicine will be able to overcome low levels of patient activation by allowing patients to get care in their home area.*

3) Background

Each year, more than 185,000 patients with PAD, DM, or combined PAD/DM undergo leg amputation. Costs to treat wounds and ulcers currently approach \$25 billion annually and are expected to double in the next decade.^{1,2} When ulcer treatment is not effective, amputation is the outcome and currently, 1.4 million people live with an amputation in the United States.^{3,4} Predictors of higher amputation rates include worse ankle-brachial index,⁵ African-American race⁶, lower socio-economic status, dialysis dependence, and older age.⁷⁻¹⁰ Patients living in rural areas are 51% more likely to undergo amputation than those in urban areas.^{11,12}

Patients residing in rural areas face numerous barriers to care. Their concerns are poorly understood, however, these patients are typically of lower socioeconomic status and have limited knowledge of chronic diseases which results in lower patient activation. The distance and burden of coordinating travel, time off work, and need to attend multiple clinic visits can be impossible for patients and families. The hardships patients endure in an effort to attend remote appointments results in unrealistic patient expectations, physician dissatisfaction, non-compliance with treatment, increased hospitalizations, and lower patient activation in disease management.

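### Both secondary Kaplan-Meier curves are limited to patients treated at UCD, an undefined condition settled after the telemedicine visit, so they may not describe the enrolled patients

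*Combined protocol and SAP*

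**What the plan says.** The secondary analyses in the Statistical Analysis Plan include a "Kaplan-Meier analysis of time to definitive revascularization and wound healing for patients that underwent telemedicine and were treated at UCD". The plan does not define what being treated at UCD means. It does not say how these curves handle patients treated elsewhere, healed without UCD treatment, amputated or never treated.

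Other sections set no such limit:

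- Section 2, aim (b), concerns "time to definitive treatment for patients with wounds and ulcers in rural clinics".
- Section 6: "Secondary endpoints are time to revascularization, time to other specialty consultation, time to wound healing", with no reference to where treatment takes place.
- Section 7, follow-up: "All patients will be contacted every 4 weeks to determine if they have had a procedure for their leg wound (revascularization". The same sentence also asks whether the wound has healed.
- Section 7, end of follow-up: "Patients will be followed until they reach a secondary study end-point which is wound healing, amputation, or for a maximum of 12 months".
- Number of Subjects: the plan is to enrol "25 subjects at each of the 5 out of network clinics that are referred to the UC Davis Vascular Clinic for telehealth services", 125 in total.
- Section 8: "Patient care is not directed in this project and is clinical driven per standard of care".

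**The concern.** Willingness to be seen by telemedicine is an entry criterion, and the baseline questionnaire is completed on the day of the visit. Having had telemedicine therefore describes essentially everyone enrolled, and the UCD condition is a further filter. Whether a patient meets it is known only later. Patients come from out-of-network clinics and the project does not direct care, so treatment elsewhere, local healing or no procedure are all plausible.

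A Kaplan-Meier estimate needs patients without the event to stay in the risk set. Choosing the analysis set by something that happens during follow-up can break that requirement. For revascularization, the condition may be almost the same thing as the event. At stake is whether the treatment-time and healing curves describe the enrolled rural patients, as aim (b) requires, or only a group picked out by its later course.

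**Working it through.** The SAP gives no event rate, target or power for these two curves, so there is no stated figure to reproduce. Its sample-size figures concern time to consultation and bear neither way. Every rate below is an assumption. The only design input is the 12-month maximum follow-up in section 7.

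**1. Revascularization, with treated meaning revascularized at UCD.** Let *p* be the proportion of all patients revascularized by 12 months, with constant hazard *h* = −ln(1 − *p*)/12 per month. Among those with the event by 12 months, the median solves 1 − exp(−*ht*) = *p*/2, so *t* = −ln(1 − *p*/2)/*h*. The whole-cohort median is ln 2/*h*.

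| *p* | *h* per month | Subset median | Whole-cohort median (extrapolated) |
|---|---|---|---|
| 0.2 | 0.0186 | 0.1054/0.0186 = 5.7 months | 37 months |
| 0.3 | 0.0297 | 0.1625/0.0297 = 5.5 months | 23 months |
| 0.4 | 0.0426 | 0.2231/0.0426 = 5.2 months | 16 months |

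Every whole-cohort median lies beyond follow-up, so it would be reported as not reached. The subset curve reaches 100% by construction. Doubling *p* from 0.2 to 0.4 moves the subset median by only 0.5 months.

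A simulation with a different structure agrees. It assumes a 16-week median among patients ever revascularized, 52 weeks of follow-up and a share never revascularized. The subset median stays near 13.6 weeks throughout. In all patients it is 16.0 weeks if none are never revascularized, 22.7 if 20%, 41.4 if 40%, and not reached if 60%. Moving a further 20% to treatment elsewhere at the same speed leaves these medians essentially unchanged, so dropping patients treated elsewhere has no built-in direction.

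**2. Either curve, with treated meaning under UCD care.** Patients without the event can now stay in as censored. With a 26-week median and 60% selected independently of the hazard, the subset median is 26.1 weeks against 26.0 in all patients. With patient-specific hazards, and a chance of selection that rises with the hazard, it is 25.5 against 37.2 weeks. Bias therefore depends on whether selection relates to outcome.

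**3. Healing, with treated meaning revascularized at UCD.** Assume a 26-week median healing time without a procedure, revascularization at UCD with a median of 8 or 16 weeks unless the wound heals first, and a healing hazard multiplied by 1, 2 or 3 afterwards.

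| Median to procedure | Multiplier | All patients | UCD-treated only |
|---|---|---|---|
| 8 weeks | 1 | 26.0 weeks | 35.6 weeks |
| 8 weeks | 2 | 17.8 weeks | 22.4 weeks |
| 8 weeks | 3 | 14.7 weeks | 17.7 weeks |
| 16 weeks | 1 | 25.9 weeks | 40.5 weeks |
| 16 weeks | 2 | 20.0 weeks | 27.0 weeks |
| 16 weeks | 3 | 17.5 weeks | 21.9 weeks |

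The subset looks slower in all six cases. Early local healers are removed, and anyone kept must have stayed unhealed until the procedure (immortal time). These scenarios include no separate group of poor healers who never have a procedure. Dropping such a group would push the other way.

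**The case against.** The strongest reply concerns wording. The SAP names the event as definitive revascularization but uses the broader word treated for the population, and one clause governs both curves. Being under UCD care fits that at least as well as having had a procedure there. On that reading patients without a procedure remain as censored, and step 2 shows no bias if selection is unrelated to outcome. This stands as a limit on the claim: the near-certain bias in step 1 belongs to one reading only. It does not rescue the text, because the term is undefined, enrolled patients are still left out, and selection driven by clinical decisions may well relate to outcome.

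A reader might infer that both curves look too fast. The documents do not support that for healing, where the exclusions pull in opposite directions. A reader might also infer that healing in the home area disappears from the plan. It does not: the chi-squared analysis of the proportion healed in the telemedicine group has no UCD restriction. The consequence is narrower, namely that healing is reported on two different populations.

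The size in step 1 is also open to challenge. The comparison ignores that follow-up stops at healing or amputation. Diabetes without PAD is sufficient for entry, so a median that is not reached may mix delay with patients who would never need a procedure. Both points stand. They are reasons to handle competing events explicitly, not to keep the filter.

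**Conclusion.** The restriction conflicts with the plan's own endpoints, with aim (b) and with follow-up of all patients, and it should be removed before analysis. For revascularization it makes times look too short if treated means revascularized at UCD; the step 1 figures rest on a constant hazard and assumed rates. Under the wider reading the bias is conditional and its size unknown. For healing the net direction cannot be stated.

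This should be fixed, but it does not threaten the trial's main result. The curves are secondary, with no stated test, alpha or power, and time to specialty consultation is untouched. It would also go too far to say that the filter alone prevents an answer on treatment time. Section 2 hypothesizes a 50% reduction, the SAP heading says the comparison arm was removed, and the only historical median given (9 weeks) is for consultation. A curve in all enrolled patients would describe them validly and still have nothing to be compared with.

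**What to change.** In the Statistical Analysis Plan:

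1. Replace the UCD condition with all enrolled telemedicine patients, measured from a stated time zero that is the same for everyone.
2. Count revascularization or healing at any facility.
3. Use cumulative incidence in place of plain Kaplan-Meier. Treat amputation and death as competing events for both endpoints, and healing as a further competing event for revascularization, because follow-up stops there.
4. Report site of treatment, or a UCD-treated subset with a written definition, only as description.

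In section 7, add the date of the event and the facility to the items recorded at the 4-weekly contacts. The text asks whether each event has occurred but mentions neither.

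The cost is a short change to the SAP and two extra items at contacts already planned for all patients. The small downside is that dates of events elsewhere rest on patient report and may be coarse. The missing comparator for the 50% reduction needs its own decision.

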
In February 2016 focused guidelines for assessment of ulcers were published as a joint effort by the Society for Vascular Surgery, American Podiatric Medical Society, and Society of Vascular Medicine. Implementation of these guidelines

PROTOCOL TITLE: Implementation of Telemedicine for patients with wounds and ulcers.

has been poor, especially in rural areas. Telemedicine improves access to expert specialty consultation and patient-centered care in the ambulatory settings. Implementation of telemedicine combines involved faculty with a team-building mentality, concise web-based tools for incorporation into daily practice, and specialty consultation. Telemedicine has been effective in psychiatry, pediatrics, dermatology, and cardiovascular diseases. In telemedicine wound programs for the treatment of ulcers in other countries, physicians found images at remote consultation showed a high concordance compared to in-person evaluation and providers were successful at making wound care recommendations based on images.

The NHLBI strategic vision prioritized community-based effectiveness and implementation research strategies to address health inequalities. Multiple countries have implemented telemedicine wound care programs to improve cost effectiveness of treatment. These programs decreased costs for transportation to provide wound care by 46%. Extrapolation to US wound care costs could indicate a potential savings of nearly \$15 billion annually by implementing a national telemedicine treatment program for ulcer management.

The Vascular Clinic at UC Davis currently conducts telehealth medical visits as a part of the general referral program at UC Davis Health. Within this referral program the clinic works with several Rural Health Centers (RHC) in California and utilizes telehealth medicine as a part of the referral process. This research study proposes to examine the information that is collected during these visits the primary endpoint for this study is time to specialty consultation

4) Inclusion and Exclusion Criteria

Patients will be identified by the clinic when they come in for their regular visit.

Inclusion Criteria

1. 18 years or older
2. Have a wound or ulcer for more than two weeks.
3. Have a diagnosis of Diabetes Mellitus (DM), Peripheral Artery Disease (PAD), vascular disease, or combined PAD/DM
4. Willing to see a provider by telemedicine
5. Able to complete the Patient Activation Measurement (PAM) survey

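### Kaplan-Meier is planned for healing and revascularization with no censoring or competing-event rule, while follow-up ends at healing or amputation; if those exits are censored, the curves overstate both shares

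*Combined protocol and SAP*

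**What the plan says.** The Statistical Analysis Plan gives two analyses of these outcomes. One is a "chi-squared analysis of the proportion of patients that had wound healing in the telemedicine group" against patients without a telemedicine visit. The other is "Kaplan-Meier analysis of time to definitive revascularization and wound healing for patients that underwent telemedicine and were treated at UCD".

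Section 7, under follow-up after the telehealth visit, sets the observation period: "Patients will be followed until they reach a secondary study end-point which is wound healing, amputation, or for a maximum of 12 months". At each 4-weekly contact the team is to "determine if they have had a procedure for their leg wound (revascularization) and if the wound has healed".

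Section 6 lists time to revascularization and time to wound healing as secondary endpoints. It also lists amputation separately and more narrowly: "number of telemedicine visits, major amputation, number of hospitalizations, number of emergency room visits, and number of in person visits".

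No section says how an amputated patient enters the healing curve, or how a patient who heals or loses the limb first enters the revascularization curve. Death is not mentioned, and no cumulative incidence method is named.

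**The concern.** The stopping rule creates exits that compete with the outcomes. An amputee is no longer followed for healing. A patient who heals without a procedure is no longer followed for revascularization. When Kaplan-Meier is the only method named, the usual programming censors a patient at last contact unless the event has occurred. The estimator then treats that patient as someone who would later have the event at the same rate as patients still followed with an open wound. That is untrue of an amputated limb and doubtful for a healed one.

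Revascularization is potentially the more exposed curve, because both healing and amputation end follow-up. Healing without a procedure is plausible, since section 4 admits patients who "Have a diagnosis of Diabetes Mellitus (DM), Peripheral Artery Disease (PAD), vascular disease, or combined PAD/DM", so diabetes alone is enough.

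Aim b in section 2 is to "improve time to specialist evaluation and time to definitive treatment for patients with wounds and ulcers in rural clinics". For the definitive-treatment half of that aim this curve is the only named analysis, with no test and no historical value beside it. If a median is read from it, it could be one that fewer than half of patients reach. The healing curve could also disagree with the healed proportion reported next to it.

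**Working it through.** **The plan's own figures.** None is given for healing or revascularization. The only power figure concerns the primary endpoint. It reproduces: 24 × 0.44 = 10.56, rounded to 11 events, and power of about 0.894 against the stated 89.2%. It has no bearing on this point.

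**Inputs.** From the documents: Kaplan-Meier, the stopping rule, the 12-month maximum and the 4-weekly contact. Assumed, because the documents give no rates: the 12-month share *p* with the event, the 12-month share *c* leaving first through a competing event, and constant hazards.

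**Formulas**, with time scaled so that 12 months = 1:

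- total hazard = −ln(1 − p − c)
- event hazard = total × p/(p + c)
- 1−KM, with competing events censored = 1 − exp(−event hazard)

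**Worked example, healing, p = 60%, c = 10%.** Total = −ln(0.30) = 1.204. Event hazard = 1.204 × 0.60/0.70 = 1.032. 1−KM = 1 − exp(−1.032) = 64.4%, which is 4.4 points too high.

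**Healing (amputation competes): excess of 1−KM, in points**

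| Truly healed | 5% amputated | 10% | 20% |
|---|---|---|---|
| 40% | 1.2 | 2.6 | 5.7 |
| 60% | 2.1 | 4.4 | 10.1 |
| 70% | 2.6 | 5.5 | 13.3 |

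**Revascularization (healing or amputation first): excess of 1−KM, in points**

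| Truly revascularized | 5% leave first | 10% | 20% | 30% |
|---|---|---|---|---|
| 20% | 0.6 | 1.2 | 2.5 | 4.2 |
| 30% | 0.9 | 1.8 | 4.0 | 6.8 |
| 50% | 1.6 | 3.4 | 7.7 | 13.4 |

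**A bound that does not need constant hazards.** With complete follow-up of *n* patients, *H* healed and *A* amputated, 1−KM lies between H/n and H/(n − A). The largest relative excess is therefore 1/0.95 − 1 = 5.3%, 1/0.90 − 1 = 11.1% and 1/0.80 − 1 = 25.0% at 5%, 10% and 20% amputated, whatever the size of the set.

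**Median.** 1−KM reaches 50% by 12 months when only 46.9%, 43.6% or 40.2% are truly revascularized, with 10%, 20% or 30% leaving first.

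**If healed patients can still be revascularized.** Take p = 40% and c = 30%, all of it healing. Total = −ln(0.30) = 1.204, event hazard = 1.204 × 0.40/0.70 = 0.688, and 1−KM = 49.7%. The true 12-month share is 40.0% if healed patients are never revascularized, 42.9% if they are at a quarter of the open-wound rate, and 45.5% at half. Kaplan-Meier is right only if the two rates are equal.

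**Coarse dating.** Dating events only at the 4-weekly contact (13 equal intervals, events before censoring in ties) shrinks the excess slightly: 4.4 to 4.1 points for healing 60% with 10% amputated, and 6.8 to 6.2 for revascularization 30% with 30% leaving first.

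**The case against.** The strongest reply is that the plan never says these patients will be censored. Ending contact at a known terminal state does not dictate censoring, and an analyst could carry amputees forward to 12 months as not healed. That stands. A reader might infer that the plan commits to a biased estimate; the documents show only that the rule is unwritten and that the one method named leads there by default.

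The size is also open. For healing, only amputation and death compete, and at 5% amputated the excess is 1.2 to 2.6 points. A reader might take the double-digit figures as expected; nothing in the documents supports 20% amputation or 30% leaving first. If being treated at UCD means vascular treatment there, few in the set would heal without a procedure and the revascularization excess nearly vanishes. The set's size is not stated. At 24 patients, the sample in the power calculation, the standard error of the 12-month estimate is about 12 points, well above the bias in the milder settings.

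The SAP promises neither a median nor a 12-month share from these curves, so misuse of the median is a possibility and not a planned step. A reader might also infer that nothing after healing can be known. Section 7 ends study follow-up at that point, but the documents do not say whether UCD clinic records would be consulted.

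None of this supplies the missing rule. The direction is not in doubt if competing exits are censored, and imprecision in a small set does not justify choosing an estimator of a different quantity.

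**Conclusion.** The concern holds in conditional form. Section 7 and the SAP together leave the handling of competing exits unwritten. If they are censored, 1−KM cannot fall below the share who actually have the event under complete follow-up, and exceeds it whenever a censored patient leaves before a later event. For revascularization this further requires that healed patients are revascularized less often than those with open wounds.

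Under assumed constant hazards the 12-month excess is about 1 to 5.5 points for healing of 40% to 70% with 5% to 10% amputated (up to 13 at 20%). For revascularization of 20% to 50% with 5% to 30% leaving first it is about 0.6 to 13 points, and near zero if few in the analysed set leave that way.

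A reader might infer that the trial's main result is compromised. It is not: both curves are secondary and descriptive, and neither time to specialty consultation nor the planned healed proportion is touched. The change is worth making because it is cheap and the revascularization curve is the only named analysis of part of aim b. Confidence is medium, since every rate is assumed.

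**What to change.** **SAP.** Replace Kaplan-Meier for these two outcomes with Aalen-Johansen cumulative incidence, with 95% confidence intervals at 6 and 12 months, and state the number of patients treated at UCD.

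- Healing: major amputation and death are competing events.
- Revascularization, defined as a procedure for the index leg wound: healing without revascularization, major amputation and death are competing events.
- Only loss of contact and end of study are censored. The latter matters because section 5 closes data collection on 12/31/2021, so late entrants will have under 12 months.

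**Section 7.** In the stopping rule change only amputation to major amputation, which matches section 6. Keep healing and 12 months as stopping points. Record the level and date of any amputation, and the date of death, at the 4-weekly contact already planned.

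**Cost.** SAP wording, one word in the stopping rule, and two items added to an existing contact; no new patients or clinic visits. Patients with a minor amputation need a few extra contacts. The estimates will be lower than, and not directly comparable with, published Kaplan-Meier curves, which the report should say.
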